17.7 Statistical/analytical issues

17.7.1 Adjustments for covariates

No adjustments for covariates will be performed.

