HIV, Hepatitis B and C test	Х		
Drug screen	X ⁴	X ⁴	
CO measurement	Х	X	
Pulse rate	X ⁵	X ⁶	
Visual Analogue Scale		X ⁶	
Investigational Product administration		X	
Collection of pouches		X	
PK blood sampling		X ⁷	
Baseline Symptoms	Х	X ⁸	
Adverse Events		X	X

Table 1 Overall Schedule of Events

¹ Visit 1 could be performed during 2 days

² Refer to Schedule of Events per visit for details.

³ Female subjects only

⁴ Drug tests during the treatment period may be performed randomly.

⁵ Before and 15 min after application of the subject's usual brand and amount of Swedish snus

⁶ Before and 5, 10, 15, 30 and 60 min after application of the investigational products

⁷ Before and 5, 10, 15, 30, 60, 90, 120, 240 and 360 min after application of the investigational products

⁸ Only prior to dose administration on visit 2.

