10.6 Restrictions during the study

- 1. Subjects shall be abstinent from snus and all other nicotine containing products from 8.00 p.m. the night before each trial day.
- 2. Subjects shall abstain from smoking the last 24 before each study day.

- 3. The subjects are not allowed to eat or drink, or use any other mouth related procedure (e.g. tooth brushing) 30 minutes before dose administration, during application of investigational products and 30 minutes after the investigational product have been taken out. [5].
- 4. Other therapy considered necessary for the subject's welfare may be given at the discretion of the Investigator. All such therapy must be recorded in the Case Report Form.
- 5. The female volunteers are expected to be sexually abstinent or use contraceptives to prevent pregnancy during the study period
- 6. Consumption of grapefruit and/or grapefruit containing products is not allowed 1 week before IP dosing until last PK day.
- 7. Xanthine or taurine containing products/beverages, e.g. Redbull, are not allowed during the study.
- 8. Abstain from drugs of abuse from Screening to Follow-up visit.
- 9. The subjects must not donate blood or plasma during the study until three months after the Follow-up Visit.
- 10. Study subjects are not allowed to participate in any other clinical study during the study period.

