12.2 Visits after Investigational product administration

The subjects should certify abstinence before each treatment is started. A detailed list of event after the administration of the investigational product is displayed in Table 2 below.

EVENT	COLLECTION OF PLASMA SAMPLES	PULSE RATE	VAS ASSESSMENT	COLLECTION OF USED POUCH SAMPLE (±1 MIN)	AE INTERVIEW
Predose	\checkmark	\checkmark	\checkmark		\checkmark
5 min	\checkmark	\checkmark	\checkmark		
10 min	\checkmark	\checkmark	~		
15 min	\checkmark	\checkmark	\checkmark		
30 min	\checkmark	\checkmark	~		
60 min	\checkmark	\checkmark	\checkmark	\checkmark	
90 min	\checkmark				
2 hrs	\checkmark				
4 hrs	\checkmark				
6 hrs	\checkmark				\checkmark

Table 2 Detailed Schedule of Events, Visit 2-6.

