12.5 Study assessments

12.5.1 Pharmacokinetics assessments

Nicotine plasma concentrations are determined at preset time points, before (0), 5, 10, 15, 30 and 60 minutes, and 1.5, 2, 4 and 6 hours after administration. Frozen plasma samples collected for nicotine determinations will be shipped to a certified contract laboratory The analysis of the plasma samples will be performed by a validated LC-MS/MS assay at ABS Laboratories Ltd, UK. To quantify nicotine a multilevel calibration at eight concentrations will be performed over a range of 0.5 to 100 ng/mL. The calibration line will be fitted by means of linear regression weighted by 1/concentration2. The samples will be assayed once. Incurred sample reproducibility will be performed according to the EMA and FDA guidelines so that 10% of the analysed study samples up to 1000 will be reanalysed and then 5% of the number above 1000. The analysis batch acceptance criteria will be: The calibration standards must have a back-calculated accuracy within $100 \pm 15\%$, except at the lower limit of quantification (LLOQ) where it must be within $100 \pm 20\%$. The standard curve must be constructed from at least three quarters (i.e. 12) of the calibration standards, excluding the zero concentration calibration standards. Duplicate quality control samples at low, medium and high concentrations will be included in each analysis batch. The accuracy of at least two thirds of the quality control samples must be within $100 \pm 15\%$. Half of the quality control samples at each concentration must be within $100 \pm 15\%$. At least half of the blank samples with internal standard and half of the blank samples without internal standard, placed immediately before the calibration standards, must be free of interference. Overall two thirds of the total number of blank samples must be free of interference. Interference is defined as a detectable response, at the retention time of the analyte, greater than 20% of the mean response of the lowest concentration (LLOQ) standards. WinNonlin computer program (Certara Corp., USA) will be used for pharmacokinetic calculations. Main variables will be AUC_{inf}, C_{max}, T_{max}.

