17.6 Analysis of secondary endpoints

The mean + SD extracted dose of nicotine from each pouch, will be calculated. The extracted dose of nicotine will be analyzed using the signed Wilcoxon rank sum test and Students t-test for within subject difference. The correlation between the AUC and the total amount of nicotine extracted from the pouch will be analyzed using Proc corr. in SAS.

The mean + SD of AUCinf based on plasma concentrations of nicotine after administration of of each pouch, will be calculated. AUC60min, Cmax, Tmax, AUCo-t and terminal half-life will also be calculated.

AUC60min, Cmax, Tmax, AUCo-t and terminal half-life of a novel, non-tobacco-based nicotine pouch to that of a Swedish snus pouch will be described using summary statistics and analyzed using signed Wilcoxon rank sum test for within subject difference.

Pulse rate and VAS for measure of subjective "head buzz" (head rush, "hit", feeling alert, overall "product strength"), will be summarized by treatment and period using descriptive statistics.

The intra subject difference of pulse rate will be analyzed using the signed Wilcoxon rank sum test and Students t-test for within subject difference.

The intra subject difference of VAS scales for "head buzz" (head rush, "hit", feeling alert, overall "product strength") will be analyzed using the signed Wilcoxon rank sum test and Students t-test for within subject difference.

All AE data will be fully listed by Investigator terms and MedDRA Preferred Term (PT). AE data will be summarized by System Organ Class (SOC) and PT.

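### Predose nicotine, pulse and VAS are measured at every treatment visit, but section 17.7.1 bars their use as covariates and no PK endpoint is defined as corrected for residual nicotine

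*Protocol*

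**What the plan says.** **Data collected.** Table 1 (protocol section 9.1) schedules plasma sampling at visits 2 to 6 "Before and 5, 10, 15, 30, 60, 90, 120, 240 and 360 min after application of the investigational products", and pulse and VAS "Before and 5, 10, 15, 30 and 60 min after application of the investigational products". Table 2 (section 12.2) confirms all three at predose.

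**Abstinence.** Section 10.6 requires: "Subjects shall be abstinent from snus and all other nicotine containing products from 8.00 p.m. the night before each trial day". Section 12.2 adds: "The subjects should certify abstinence before each treatment is started". Table 1 allows a wash-out as short as one day. The exhaled CO test belongs to the definition of a smoker in section 10.5; no objective check of snus abstinence is described.

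**PK endpoints.** Section 12.5.1 gives the sampling times ("Nicotine plasma concentrations are determined at preset time points, before (0), 5, 10, 15, 30 and 60 minutes", then up to 6 hours) and an assay calibrated "over a range of 0.5 to 100 ng/mL". Sections 8.1.1, 12.5.1, 17.5 and 17.6 describe the PK endpoints without calling them corrected or uncorrected for the predose level.

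**Analysis.** Section 17.5 compares AUCinf by a within-subject signed-rank test. Section 17.6 reports mean and SD of AUCinf for each pouch, summarises and tests the other PK parameters, and correlates AUC with extracted nicotine. For pulse it says: "The intra subject difference of pulse rate will be analyzed using the signed Wilcoxon rank sum test and Students t-test for within subject difference". VAS is treated the same way. Section 17.7.1 then states: "No adjustments for covariates will be performed".

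**The concern.** A predose sample from a habitual user measures what the subject brought along. Nicotine left from the subject's own snus keeps decaying during the session, and its area is counted in AUC and Cmax unless it is removed. Section 7.1 gives the main aim as documenting extraction from ZYN and the resulting systemic uptake, so the level for each product matters as well as the contrast with snus.

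Pulse and VAS also start from a level that can differ from visit to visit. The same-visit predose value is the natural means of removing that variation, and it is already collected. Section 17.7.1 excludes it as a covariate. With 18 subjects, avoidable noise is worth removing.

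**Working it through.** The plan gives no figure on this point. Its only computed figure, a sample size of 16, concerns extracted nicotine and does not enter here. The documents give no half-life, predose level or AUC, so all inputs below are assumptions unless marked.

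**1. Area added per period.** Under first-order decay with half-life h, a predose level C0 adds
- to AUCinf: C0 × h / ln 2
- to AUC60min: C0 × (h / ln 2) × (1 − 2^(−1/h))
- to Cmax: at most C0

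Results at the two ends of the assumed range:
- C0 = 0.5 ng/mL, h = 1.5 h: AUCinf + 0.5 × 1.5 / 0.693 = 1.1 ng·h/mL; AUC60min + 0.4.
- C0 = 3 ng/mL, h = 4 h: AUCinf + 3 × 4 / 0.693 = 17.3 ng·h/mL; AUC60min + 2.75.

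**2. Is such a C0 plausible?** Take 12 h of full abstinence (8 p.m. is from the protocol; 8 a.m. dosing is assumed) and an 8 p.m. level of 10 to 30 ng/mL. Then C0 = level × 2^(−12/h):

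| h | C0 (ng/mL) |
|---|---|
| 1.5 h | 0.04 to 0.12 |
| 2 h | 0.16 to 0.47 |
| 3 h | 0.6 to 1.9 |
| 4 h | 1.25 to 3.75 |

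At 2 h or less, C0 lies below the lowest calibration level of 0.5 ng/mL (section 12.5.1). A lapse changes this. A level of 15 ng/mL at midnight leaves, 8 h later, 15 × 2^(−4) = 0.9 ng/mL (h = 2 h) or 15 × 2^(−8/3) = 2.4 ng/mL (h = 3 h).

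**3. Effect on the paired difference.** Product order is randomized, so the residual has the same expectation under every product and its mean cancels. A simulation (18 subjects, mean C0 2 ng/mL, h = 2 h) gave a mean shift of 0.00 to 0.01 ng·h/mL. What remains is noise. If s is the visit-to-visit SD of C0, the SD added to the AUCinf difference is √2 × s × h / ln 2:
- s = 0.5 ng/mL: 1.414 × 0.5 × 2.885 = 2.0 ng·h/mL
- s = 1 ng/mL: 1.414 × 1 × 2.885 = 4.1 ng·h/mL (3.9 in the simulation, which kept levels non-negative)

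This combines in quadrature with the other variation. Without an SD for AUC differences in the documents, no loss of power can be computed.

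**4. Effect elsewhere.** Per-product means get no help from randomization: mean AUCinf rises by the average of the amounts in step 1. The residual area is unrelated to what leaves the study pouch, so it adds variance to AUC without adding covariance with extraction, and the correlation shrinks toward zero.

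**5. Pulse and VAS.** No arithmetic is possible, because no variance or within-visit correlation is given. Sections 9.1, 17.6 and 17.7.1 read together show that the predose values exist, that the tests are unadjusted, and that covariate use is excluded.

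**The case against.** **Section 17.7.1 is about the statistical comparison.** A reader might infer that it rules out baseline correction of the PK parameters, so that residual nicotine must enter uncorrected. The text does not support that. Removing residual nicotine is a step in deriving AUC and Cmax, which section 17.7.1 neither covers nor forbids. The protocol is silent, and section 17 calls itself an outline to be completed by a SAP. Silence on a derivation rule is therefore no error in itself. This objection stands.

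**The paired design protects the comparison.** A reader might also infer that residual nicotine systematically favours one product, or that it distorts a ratio to snus. The planned tests use within-subject differences, where the mean residual cancels, and the protocol plans no ratio analysis. This stands too, for the differences only. It does not cover the per-product means or the correlation.

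**The residual may be negligible.** With strict abstinence and fast elimination it is below the assay range. This is fair, and the documents cannot settle it.

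**Pulse may already be a change from predose.** The within-subject difference in section 17.6 is undefined and could mean that, so it cannot be said that predose pulse goes unused. Even so, a change score fixes the predose coefficient at 1. Letting the data estimate it is what section 17.7.1 excludes, and that exclusion is explicit.

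**Conclusion.** The point holds as a cheap improvement, not as a flaw that undermines the primary comparison. Section 17.7.1 bars the collected predose pulse and VAS values from use as covariates, and the protocol leaves open whether the PK endpoints are corrected for residual nicotine.

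Uncorrected, the residual would cost precision in the paired differences, inflate mean AUC and Cmax for each product, and weaken the AUC-extraction correlation. It would not bias the planned differences on average. The added AUCinf could be about 1 to 17 ng·h/mL per period, or close to nothing. That range rests wholly on the assumed half-life and predose level, and its upper end needs slow elimination or incomplete abstinence.

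**What to change.** 1. **Pulse and VAS.** Amend section 17.7.1 to allow the same-visit predose value as a covariate. For example, at each time point regress the within-subject product difference on the difference in predose values; the intercept is the adjusted product effect. Keep the planned paired tests as supportive.
2. **PK endpoints.** State that AUCinf, AUC0-t, AUC60min and Cmax are derived from C(t) − C0 × exp(−λz × t) when the predose level is quantifiable, with λz from the same period. For AUCinf this amounts to subtracting C0 / λz. Report uncorrected values as sensitivity.

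**Cost.** Analysis programming and wording only; every value needed is already collected. The change to section 17.7.1 needs a protocol amendment under section 14.5 and should be settled before the database closes. The downside is that the correction depends on the estimated terminal slope, and only the samples at 1.5, 2, 4 and 6 h follow removal of the pouch. The uncorrected sensitivity analysis shows how much this matters.

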17.7.2 Handling of dropouts or missing data

Missing data will not be imputed.

17.7.3 Multiple comparison/multiplicity

Even though many pairwise comparison will be made, will no p-value adjustments will be enforced. However, a medical/clinical judgement will be applied to all significance tests, in order to avoid any conclusions based solely on statistical significance and without any clinical relevance.

17.7.4 Examination of subgroups

No subgroup analysis will be performed.

